# 3) Objectives\*

The study described in the protocol is a randomized trial at UM. The study will enroll 100 11-18 year old youth with a self-reported act of self-harm in the past 6 months and their families. This study is designed to refine and test the efficacy of a computer assisted culturally informed and flexible/adaptive intervention for Latino adolescents for whom self-harm behaviors are a health disparity—specifically, Latinas and sexual/gender minority youth. The specific aims of this study are:

- To build on the Computer Assisted CIFFTA intervention by creating a web-site and web-based delivery system and by adding content that is relevant for the factors that maintain self-harm in Latina adolescents (e.g., depression, family conflict, substance use, and emotion dysregulation) and for unique stressors often linked to sexual/gender minority youth and those exposed to trauma.
- 2) To investigate the preliminary efficacy of the Computer Assisted CIFFTA in reducing self-harm and in modifying the factors that place youth at risk for self-harm (e.g., depression, family conflict, substance use, and emotion dysregulation) when compared to controls (Treatment-As-Usual).
- 3) To investigate the linkages between co-existing problem areas (e.g., selfharm, risky sexual behavior, substance use) to see if there is evidence of a syndemic.
- 4) To investigate the relationship of culture-related variables (e.g., acculturation, familism, and Hispanic Stress) to the key factors hypothesized to contribute to self-harm behavior (i.e., depression, family conflict, substance use, and emotion dysregulation).

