## 9) Study Endpoints\*

- 1. Primary
  - a. Self-harm
- 2. Secondary:
  - a. Depression
  - b. Family functioning
  - c. Alcohol/substance use
  - d. Emotional dysregulation
  - e. Risky sexual behaviors

There are no safety endpoints in this study.

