Adaptations for youth who report being LGBTQ and/or exposed to trauma, and families. CIFFTA's design lends itself to adaption to diverse populations. Its logic and emphasis on tailoring facilitates the treatment's extension to new populations with unique stressors. During the development phase of this study (first 7 months) we will build on existing modules. Some of the expected adaptations will focus on modules for kids on how they can cope with stressors related to LGBT-related rejection and alienation, emotion regulation and distress tolerance for ameliorating self-harm behaviors, using evidencebased coping strategies for risk factors result from exposure to traumatic events (see Seeking Safety strategies). A module for parents who are having a hard time accepting their son's/daughters being a gender/sexual minority youth will help them to understand the normative stages some parents must go through, allow parents to express their concerns, distress, and fears, so that they are more ready to have a productive family therapy session with their sons and daughters. A parallel module may be offered to youth to increase their readiness to have a family session in which a loving and caring relationship can be created.

Measures: Measures have been selected for: 1) Screening; 2) Ultimate Adolescent Outcomes, e.g., Self-harm; 3) Immediate Outcomes, e.g., depression, emotion regulation, family conflict, and substance use; 4) Cultural Factors; and 5) Additional Measures, e.g., trauma, minority stress. Measures will be administered at Screening, Baseline (T1) 4 months after baseline (Termination or T2), and 12 months after baseline (T3). Spanish versions of the measures are available. Every effort has been made to reduce participant burden. The total battery is expected to take 90 minutes to administer to youth and 40 minutes to parents. These will be administered in person or via HIPAA compliant Zoom. Measures are attached.

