NCT03709472

Computer Assisted Family Intervention to Treat Self-Harm Disparities in Latinas and Sexual/Gender Minority Youth

Statistical Analysis Plan 8/21/24

Data were analyzed using SPSS Version 29 (IBM, 2023). We began our analyses by documenting the number of session and hours of treatment to assess CIFFTA's feasibility and acceptability. We conducted logistic regressions to examine whether baseline characteristics predicted those participants who successfully reached termination and T2 assessments. To examine whether changes in adolescent symptoms of depression over time differed by treatment, a mixed ANOVA was used with depression scores as the within-subjects variable and treatment condition as the between-subjects variable. We used the same analytic strategy to determine whether changes in emotion regulation and family connectedness differed over time by treatment. A series of mixed ANOVAs were used with the Total scores from the PHQ-9, the Difficulty with Emotion Regulation Scale and the Family Connectedness Scale as the within-subjects variables and treatment condition as the between-subjects variable. When effect sizes are reported, cutoffs for partial eta-squared effect sizes are small .01, moderate .06, large .14. Additionally, Chi-Square Tests of Association were used to determine whether the proportion of youth endorsing whether they could talk to their parent about problems differed over time. This analysis was conducted by condition examining mothers and fathers separately.

A complementary analytic strategy was used to investigate change in youth who entered the study with presenting problems in the clinical range at baseline assessments based on established clinical cutoffs (i e., those with at least mild levels of depression at baseline). Descriptive statistics were used to determine the rates of suicidal thoughts and self-harm at baseline and termination by condition. In addition, Chi-Square Tests of Association were used to determine whether the proportion of youth endorsing thoughts of suicide differed by treatment condition.

We also used the Reliable Change Index (RCI) to determine whether the magnitude of change was statistically reliable rather than due to random fluctuations caused by measurement error (Jacobson & Traux, 1991). We examined symptoms of depression.

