Lastly, to examine whether changes on the plausible mechanisms of action was associated with the likelihood of engaging in self-harm in the past month at termination in the full sample; after controlling for gender and LGBTQ status, a series of hierarchical logistic regressions were performed. With only two timepoints we could not conduct formal analyses of mediation, but we could explore whether the patterns of change were consistent with plausible mediators. In these models, self-harm in the past month was the binary outcome variable, LGBTQ status and gender were entered in Step 1 as covariates, and the proposed mechanism of action (i.e., depression, parent communication, family connectedness, and emotion regulation) were entered in Step 2.

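### The two-timepoint mixed ANOVA on three secondary scales is a change-score t-test: valid, but usually less precise than ANCOVA on the baseline score already collected

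*SAP*

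**What the plan says.** The SAP compares the arms on depression by a mixed ANOVA: "a mixed ANOVA was used with depression scores as the within-subjects variable and treatment condition as the between-subjects variable". It extends this to three scales, with the "Total scores from the PHQ-9, the Difficulty with Emotion Regulation Scale and the Family Connectedness Scale as the within-subjects variables". The stated question is whether change over time differs by treatment, so the test of interest is the condition-by-time interaction. The paragraph on the ANOVAs does not number the timepoints. The closing paragraph, on mechanisms of action, does: "With only two timepoints we could not conduct formal analyses of mediation".

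The SAP names one kind of effect size for these analyses: "cutoffs for partial eta-squared effect sizes are small .01, moderate .06, large .14". It names no adjusted mean difference and no confidence interval. Its only covariates, gender and LGBTQ status, belong to the logistic models for self-harm.

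Protocol section 10 (Measures) schedules T1, T2 and T3: "Measures will be administered at Screening, Baseline (T1) 4 months after baseline (Termination or T2), and 12 months after baseline (T3"). Section 10 (Screening and Assessment Procedures) puts baseline before randomisation. Section 9 lists depression, "Family functioning" and "Emotional dysregulation" as secondary endpoints; self-harm is primary.

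**The concern.** With two timepoints, the interaction test compares mean change between the arms. This fixes the weight on the baseline score at 1. ANCOVA estimates that weight from the data and targets the same arm difference, because randomisation makes the baseline means equal in expectation. If the best weight is well below 1, the change score carries baseline noise that ANCOVA would remove.

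At stake is part of aim 2 (Protocol section 3), which asks about effects "in modifying the factors that place youth at risk for self-harm (e.g., depression, family conflict, substance use, and emotion dysregulation"). With 100 youth, a wider interval makes a real difference on these scales easier to miss. Partial eta-squared also gives the reader neither the direction of an effect nor its size in scale points. Family connectedness is taken here as a measure of family functioning, for which section 9 names no scale.

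**Working it through.** **Inputs from the documents.** 100 youth (Protocol sections 6 and 25); two arms, randomised after baseline; two analysed timepoints (SAP). The documents give no SD, correlation, alpha, power or sample-size calculation, so there is no planned figure to reproduce.

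**Assumptions.** 1:1 allocation; two-sided alpha 0.05; complete data; T1-T2 correlation ρ from 0.4 to 0.8; ratio k = SD(T2)/SD(T1) of 1, 1.3 or 0.8. A ratio above 1 is possible because the entry cut-offs in section 5 may narrow the baseline spread. The main case is 50 per arm. A low case of 35 per arm borrows the roughly 70% adolescent retention that section 10 reports for an earlier trial at 16 months; T2 here is at 4 months.

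**Step 1: the planned test is a change-score t-test.** Let d = T2 − T1. The interaction contrast is the arm difference in mean d. Its sum of squares and its error sum of squares are each half of those from a one-way ANOVA of d on arm. The halves cancel, so F on 1 and N − 2 df equals t². In simulated data sets the two agreed to within 2e-14.

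**Step 2: variance per youth.** With T1 and T2 SDs s0 and s1:
- change score: s0² + s1² − 2ρ·s0·s1
- ANCOVA: s1²(1 − ρ²)
- difference: (s0 − ρ·s1)², which is never negative and is zero only when ρ·s1 = s0.

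**Step 3: finite samples.** Estimating the baseline slope multiplies the ANCOVA variance by 1 + 1/(N − 4) and costs one degree of freedom. For k = 1, ρ = 0.5 and 50 per arm:
- planned: variance 1 + 1 − 1 = 1.00; half-width 1.9845 × √(2/50 × 1.00) = 0.397 SD
- ANCOVA: variance 1 − 0.25 = 0.75; half-width 1.9847 × √(2/50 × 0.75 × 97/96) = 0.346 SD
- ratio 1.149, so the planned interval is 14.9% wider.

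At 35 per arm the half-widths are 0.477 and 0.416 SD (14.6% wider).

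Excess width of the planned 95% interval over baseline-only ANCOVA, 50 per arm:

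| ρ | k = 1 | k = 1.3 | k = 0.8 |
|---|---|---|---|
| 0.4 | 18.9% | 7.2% | 36% |
| 0.5 | 14.9% | 4.2% | 32% |
| 0.6 | 11.2% | 1.7% | 28% |
| 0.7 | 7.9% | −0.1% | 26% |
| 0.8 | 4.9% | −0.4% | 24% |

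At 35 per arm the entries are slightly lower (for k = 1, 18.6% falling to 4.6%).

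**Step 4: power.** Take k = 1, ρ = 0.5 and an assumed true difference of 0.5 SD, using the noncentral t. At 50 per arm the noncentrality is 0.5/0.200 = 2.50 (planned) and 0.5/0.174 = 2.87 (ANCOVA), giving power 0.697 and 0.811. At 35 per arm, power is 0.541 and 0.656. No power is quoted for unequal SDs, because the answer depends on whether 0.5 SD means the T1 or the T2 SD.

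**Step 5: adding the four stratification factors.** Taken as binary and predicting nothing, they change the variance factor from 1 + 1/(N − 4) to 1 + 5/(N − 8). The ANCOVA interval widens by 2.2% at 50 per arm and 3.3% at 35. For k = 1 and ρ = 0.5, the planned test's excess falls to 12.4% and 10.9%. For k = 1.3 and ρ = 0.6, the covariate-adjusted interval is already 0.5% (50 per arm) or 1.8% (35 per arm) wider than the planned one, and the gap grows at ρ 0.7 and 0.8.

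**The case against.** The strongest reply is that this is a preference between two valid methods. The SAP asks whether change differs by treatment, and a mixed ANOVA answers that directly. The scales are secondary, aim 2 is about preliminary efficacy, and no power target exists for the choice to undermine. The size of the loss rests wholly on assumed correlations and SDs, and at one end of the range ANCOVA gains nothing.

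Most of this stands and sets the weight of the point. It does not remove it: ANCOVA estimates the same arm difference with equal or better large-sample precision, from data already held.

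Four stronger readings are tempting and are not supported:
- A reader might infer that the mixed ANOVA is invalid or biased. Under randomisation with complete data it is neither.
- A reader might infer that the trial lost material power. No correlation or SD is given, so this cannot be shown.
- A reader might infer that no mean difference or interval was reported. A short SAP that names neither does not establish that.
- A reader might infer that ANCOVA would deal with missing T2 scores. It would not. In one simulated case (ρ 0.5, equal SDs, dropout in one arm depending on T2) the bias was 0.128 SD for ANCOVA and 0.085 SD for the change score. That ordering is not general: at ρ 0.8 and SD ratio 1.3 it was 0.081 and 0.086.

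The two-timepoint reading is itself an inference. The phrase is written about mediation, and the protocol schedules T3. It agrees with the SAP's other references to baseline, termination and T2.

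**Conclusion.** The point holds as an efficiency note of low severity: an optional improvement to a valid analysis. The algebra in steps 1 and 2 is certain once two timepoints are accepted. The size is not: over the assumed range it runs from a planned interval about 36% wider than ANCOVA's to one 0.4% narrower at 50 per arm. It depends on ρ, the SD ratio, the allocation ratio and the numbers analysed, none of which the documents fix. The primary endpoint, self-harm, is untouched.

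**What to change.** For each of the three scales, fit an ANCOVA of the T2 score on arm and baseline score, analysed as randomised. Report the adjusted mean difference in scale points with its 95% interval. The SAP is written in the past tense, so label this as a revised analysis and show it beside the planned mixed ANOVA; neither result should be chosen for being more favourable.

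Adding the four factors that stratified randomisation (Protocol section 10, Procedures for Phase II: gender, type of self-harm, trauma exposure, LGBT status) is optional. If they predict nothing, they cost about 2% to 3% in interval width. At an SD ratio of 1.3 that makes the interval wider than the planned one from about ρ 0.6 upward.

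The cost is one supplementary model per scale, with no new data and the same software. Reporting the observed T1 and T2 SDs and their correlation would let readers see how much precision was at stake.

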will be contacting them within 48 hours. These activities are conducted by study personnel (UM researchers) at the UM site, the IIFC or virtually via HIPAA compliant Zoom. If a participant is randomized to the control condition, a warm hand-off process will be used to connect the family to an agency staff member for the treatment. If a referral is identified by the Nicklaus Children's Hospital Inpatient Psychiatry Department staff, they will contact the youth's caregivers directly to explain the study. If the family is interested in participating in the study, the Nicklaus staff will obtain a release of information so that the UM staff can contact the youth and caregiver to sign consent, screen and assess the family. If the family is not randomized to the CIFFTA program, the UM staff and the Nicklaus staff will work together to place the youth in an outpatient program in the community. Nicklaus Children's Hospital will not be releasing any information to the UM CIFFTA program. All participants will be assessed again 16 weeks post baseline/treatment termination, and at T3: 6 months post completion of continuing care (12 months after baseline). Bachelor's/Master's level research assistants who are bilingual in English and Spanish will be available to administer all assessments. Each assessment interview lasts approximately 2 hours and consists of two parts, an interview (adolescents and parents separately) and responding to questions on the REDCap. The assessor interviews parents while the adolescent completes the REDCap battery and then they switch. The Measures appendix provides an overview of the measures, the time-points and the target of data collection. To increase participation families will be paid \$75 for T2 and \$100 for T3 completed assessments. They will receive the money either in person or cash deposits via Zelle. The fees may be slightly higher than studies that work with only one participant. The fee is meant to compensate 2-3 participants (typically adolescent and two caregivers) for 2 hours of assessment time. Interview data are entered directly into the REDCap system. In addition to the baseline assessment that all families receive at the start of the study, families will be asked to participate in an additional semi-structured interview right after the baseline (1 hour semi-structured interview for the child and 1 hour for the parent/caregiver). This interview is voluntary and asks additional qualitative questions about family functioning and self-harm to gather details on these concepts (these types of questions are asked in the baseline and follow-up assessments). To compensate for each family's time participating in these interviews, each youth will be offered a \$15 gift card to either Target or Amazon and each parent/caregiver will also be offered a \$15 gift card to either Target or Amazon.

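### Change in whether youths can talk to a parent is tested with an unpaired chi-square test within each arm: the wrong test for paired answers, and no comparison of treatments

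*SAP*

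**What the plan says.** The first paragraph of the SAP applies a chi-square test to the share of youths who "could talk to their parent about problems differed over time. This analysis was conducted by condition examining mothers and fathers separately". That makes four tests, one for each arm and parent. No paired test and no condition-by-time term is named for this item.

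The SAP words its other comparisons differently. For depression it says: "To examine whether changes in adolescent symptoms of depression over time differed by treatment, a mixed ANOVA was used", and the same strategy covers emotion regulation and family connectedness. For suicidal thoughts it tests "whether the proportion of youth endorsing thoughts of suicide differed by treatment condition".

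The design is repeated measures. In the Protocol's section 10 (Screening and Assessment Procedures): "All participants will be assessed again 16 weeks post baseline/treatment termination". The last paragraph of the SAP confirms that two time points are analysed. Aim 2 of the Protocol (section 3) is preliminary efficacy "when compared to controls (Treatment-As-Usual").

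**The concern.** There are two separate faults.

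- **Pairing.** Each youth supplies a baseline and a termination answer. A chi-square test of association assumes independent observations in the table. If the answers are stacked as visit by answer, each youth is counted twice and the standard error is wrong. If baseline answer is cross-tabulated with termination answer, the test asks whether the two answers are correlated, which they almost certainly are, and not whether the proportion moved.
- **No treatment contrast.** A significant change in one arm and a non-significant change in the other is not evidence that the arms differ.

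Parent communication is one of the mechanisms of action proposed in the SAP's last paragraph. The other three (depression, emotion regulation, family connectedness) each have a mixed ANOVA by treatment. For parent communication, these within-arm tests are the only stated analysis of whether it changed. A claim that CIFFTA improved it more than treatment as usual would have no valid test behind it.

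**Working it through.** The documents give no power calculation, significance level or response rate for this item, so there is no stated figure to reproduce. The check is of how the named test behaves.

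**Inputs**
- 100 youths (Protocol section 25). Equal allocation is assumed from the coin-flip description in section 30: 50 per arm.
- Low case: 70% of adolescent assessments were obtained in a previous trial at 16 months (section 10, Prevention of Dropouts). 0.70 × 50 = 35 per arm.
- Assumed: two-sided 5% level; 50% at both visits for no change; 40% to 60% for change; within-youth correlation φ of 0.3 to 0.5.

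**Stacked table.** With equal marginal variances v and n complete pairs, the true variance of the difference is 2v(1 − φ)/n. The chi-square uses 2v/n.
- Its standard error is therefore too wide by 1/√(1 − φ): 1/√0.7 = 1.195 and 1/√0.5 = 1.414, that is 20% to 41%.
- True size = 2[1 − Φ(1.96/√(1 − φ))]: 1.9% at φ = 0.3 and 0.6% at φ = 0.5. Simulation agrees (table).

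**Cross-table.** With no change in the proportion, the statistic has a non-centrality of about nφ². At n = 35 that is 35 × 0.09 = 3.15 and 35 × 0.25 = 8.75. The test therefore rejects often, and more often the more consistent the youths are.

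**Simulation** of paired 2×2 tables, at least 100,000 per setting, φ = 0.3 / 0.5:

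| | n = 35 | n = 50 |
|---|---|---|
| Stacked, no change: rejects | 1.6% / 0.5% | 2.2% / 0.7% |
| Cross-table, no change: rejects | 42% / 86% | 59% / 96% |
| McNemar, no change: rejects | 4.4% / 4.4% | 5.0% / 4.4% |
| Stacked, power for 40% to 60% | 34% / 31% | 55% / 56% |
| McNemar, power for 40% to 60% | 49% / 64% | 67% / 81% |

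**Within-arm testing.** If both arms truly change equally and each within-arm test has power q, exactly one arm is significant with probability 2q(1 − q), and CIFFTA alone with probability q(1 − q).
- Stacked test, n = 35: 2 × 0.34 × 0.66 = 45% and 2 × 0.31 × 0.69 = 43%.
- Stacked test, n = 50: 2 × 0.55 × 0.45, about 49%.
- Maximum, at q = 0.5: 50%, with CIFFTA alone in 25%.
- McNemar within arms: 50% / 46% at n = 35 and 44% / 31% at n = 50. Correcting the pairing does not supply the missing comparison.

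**Incomplete pairs.** The SAP does not say that only youths with both visits are used. If 50 answer at baseline and 35 of them at termination, the true variance is proportional to 1/50 + 1/35 − 2φ/50.
- φ = 0.3: 0.0486 − 0.0120 = 0.0366. The standard error is too wide by √(0.0486/0.0366) = 1.15, and the size is about 2.4%.
- φ = 0.5: 0.0486 − 0.0200 = 0.0286. The factor is √(0.0486/0.0286) = 1.30, and the size is about 1.1%.

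**The case against.** The best defence is that the SAP does not show the table layout and that its reference to condition is loose. A condition-by-answer table at each visit would be a valid independent-samples test and would compare the arms. But the stated question is change over time, which that table does not test, and the same SAP says plainly when it means a difference by treatment. If that layout was used, the text still has to be corrected.

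Several points of scale do stand.
- The 35 per arm comes from a different trial at 16 months, while this analysis is at 16 weeks, so the range up to 50 belongs in the statement.
- The 20% to 41% excess in the standard error holds for complete pairs. With partial pairing it is 15% to 30%.
- The 50% chance of a one-arm result is a maximum. The stacked test's own power gives 43% to 49%.
- The stacked error is conservative: it costs power and does not create false positives. With no change in either arm, exactly one arm is significant in only about 1% to 3% of trials.
- The item is not a named endpoint (Protocol section 9 lists family functioning), and the mechanism regressions do not use these p-values.
- Neither document says that the within-arm results will be read as an arm difference. That is a risk the design creates, not a stated intention.

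These points limit the consequence. None of them makes the named test answer its question.

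**Conclusion.** The concern holds. As written, the test is not valid for change in a proportion on the same youths under either time-based layout, and no treatment comparison is stated for this outcome. The direction of the pairing fault needs only a positive within-youth correlation. Its size rests on the assumed response rates, correlation, significance level, allocation and numbers per arm. Over the ranges used, the stacked test's size is about 0.5% to 2.4% instead of 5%. With complete pairs, its power falls 12 to 33 percentage points below McNemar's (67 − 55 and 64 − 31). The cross-table reading is uninformative about change. The missing arm comparison depends on none of these assumptions. The outcome is supportive, so the primary self-harm endpoint is unaffected, but these p-values should not be used to claim an effect on parent communication.

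**What to change.** Replace the within-arm chi-square tests with a direct comparison of the arms, for mothers and fathers separately. Two options would serve:
- logistic regression of the termination answer on arm and baseline answer, among youths with both answers; or
- GEE for the binary answer with condition, visit and condition-by-visit, clustered on youth, which can also use youths with only one answer.

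Report the risk difference between arms with its 95% confidence interval, and state how many youths contribute for each parent.

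Add the stratification factors (gender, type of self-harm, trauma exposure, LGBT status) only as far as the counts allow. All four with arm and baseline answer make at least six coefficients. With 70 youths and a 50% response, that is 35/6, about six events per coefficient. It may be fewer for fathers, since section 5 of the Protocol requires only one participating parent-figure.

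If within-arm change is still shown, use McNemar's test, in its exact form when few youths change their answer, and label it descriptive.

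The cost is a revised SAP paragraph and a re-run on the same data in the same software. Because the SAP is dated 8/21/24 and written in the past tense, the wording change alone is not enough: any results already produced for this item need recomputing, with the change recorded as made after the analysis.

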# 4) Background\*

### **Significance and Rationale**

Suicide is the second leading cause of death in youth ages 10-24, and self-harm which includes nonfatal suicide attempts (SA) and non-suicidal self-injury (NSSI)—is prevalent and is a risk factor for future suicide attempts and suicide completion. Selfharm does not typically emerge in a vacuum; it is commonly found to occur with other mental health (e.g., depression and emotion dysregulation) and behavioral (e.g., alcohol and drug use, risky sexual behavior, and externalizing behavior) symptoms. Evidence suggests that these behaviors occur in clusters as described by Syndemic theory and, if untreated, lead to severe adverse substance abuse, violence, and HIV/AIDS (SAVA) disparities in youth and other vulnerable populations. A cross-sectional investigation of high school youth found that engagement in risky sex, self-harm/cutting, and externalizing behaviors tended to co-occur among youth who reported using illicit substances. In a study with adolescents participating in an intensive psychiatric treatment program, risky sexual behaviors, including inconsistent condom use, were found to be associated with self-harm behaviors. In the treatment of these youth, research has suggested that (a) several stressors are likely to arise with non-suicidal self-injury and suicide-related injuries and (b) any program seeking to treat existing risk factors and prevent repeated self-injury and suicide should be prepared to address these stressors. Among these stressors are the marginalization experienced by sexual and gender minority youth, traumatic experiences, chronic family conflict, and alcohol use. In addition, culture-related variables may place Latinas at even higher risk due to breakdowns in family protective factors.

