## 5) Inclusion and Exclusion Criteria\*

Inclusion Criteria: To be included in the study, the adolescent must: (a) be 11 to 18 years old; (b) self-report an act of self-harm in the past 6 months, (c) meet cut-off criteria on two of the four maintaining factors (depression, emotion dysregulation, family conflict, substance use), and (d) live with at least one parent-figure who agrees to participate in assessments and treatment. Participants should be willing and able to participate fully in the protocol (e.g., to accept assignment to either condition, to provide sufficient locator information for follow-up, to allow their treatment sessions to be recorded for fidelity/process assessment and supervision). All family members in the household are invited to participate in treatment. Our success at engaging family members is evident in that an average of three family members per household participated in family intervention studies.

Exclusion Criteria: Exclusion criteria include: (a) history of DSM V Developmental Disorders, Elective Mutism, Organic Mental Disorders, Schizophrenia, Delusional Disorder, Psychotic Disorder, and Bipolar Affective Disorder. We will exclude youth who are actively in crisis and reporting current ideation with a specific plan and with means to complete the plan. If a youth is referred in this state, it will be a priority to utilize a warm-handoff procedure to connect them to a more intensive treatment program.

Eligibility Screening: Staff at the referral sites will be trained to identify youth appropriate, namely a self-harm event, for the study. When a youth/family is identified as potentially appropriate the referral site will ask the family to sign a release of information so that study personnel can contact them to schedule a formal screening. If the form is signed, the referral site will contact the designated study personnel (assessor) and provide the contact information for the family. The study personnel will contact the family and schedule an appointment to conduct the screening. When the family attends the appointment, the screening measures (Self-harm, family conflict, emotion dysregulation, depression and substance abuse) will be administered to determine eligibility. (see sections below)

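### Self-harm, the only primary endpoint, is compared between arms only through descriptive rates; the SAP describes no interval or test by arm for it

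*SAP*

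**What the plan says.** Protocol section 9 (Study Endpoints) has a single primary entry, self-harm, and five secondary ones: depression, family functioning, alcohol/substance use, emotional dysregulation and risky sexual behaviours. It names no time point. Aim 2 in section 3 (Objectives) leads with the same outcome, "To investigate the preliminary efficacy of the Computer Assisted CIFFTA in reducing self-harm", and names TAU as the comparator.

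The SAP, dated 8/21/24, is an account of completed work; it opens with "Data were analyzed using SPSS Version 29". Its second paragraph concerns youth whose presenting problems were in the clinical range at baseline. There it says: "Descriptive statistics were used to determine the rates of suicidal thoughts and self-harm at baseline and termination by condition". The next sentence adds a test by arm, for a different outcome: "Chi-Square Tests of Association were used to determine whether the proportion of youth endorsing thoughts of suicide differed by treatment condition". The closing paragraph uses past-month self-harm at termination as a binary outcome in the full sample, with gender and LGBTQ status in step 1 and the proposed mechanisms in step 2.

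**The concern.** A randomised comparison should give its primary endpoint at least the treatment it gives its secondary ones. Here three of the five secondary endpoints (depression, emotional dysregulation, and family functioning through connectedness) are tested by arm, as are thoughts of suicide. Self-harm gets rates side by side.

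The main efficacy question is therefore left without a stated contrast or any measure of its precision. A reader could work out an interval only if counts and denominators were reported for a known population. The SAP promises neither, and the position of the sentence leaves the population open. In a report built on this SAP, inferential results for secondary outcomes could carry the efficacy message while the primary endpoint has none.

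**Working it through.** **1. Each SAP analysis, checked for a between-arm result on self-harm**

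| SAP analysis | Outcome | Role of treatment condition |
|---|---|---|
| Sessions and hours | Feasibility, acceptability | Not an efficacy comparison |
| Logistic regressions on reaching termination/T2 | Retention | Not an efficacy comparison |
| Mixed ANOVAs | PHQ-9, emotion regulation, family connectedness | Between-subjects factor: tested by arm |
| Chi-square, talking to parents | Parent communication | Change over time, run within each condition |
| Descriptive rates | Suicidal thoughts and self-harm | Shown by condition; no interval or test |
| Chi-square by condition | Thoughts of suicide | Tested by arm |
| Reliable Change Index | Depression | Self-harm not covered |
| Hierarchical logistic models | Past-month self-harm, full sample | No treatment term listed |

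Self-harm appears in two rows. One is descriptive. The other relates mechanisms to self-harm across both arms together and cannot yield a CIFFTA versus TAU effect. The chi-square by condition cannot be read as covering self-harm, because the sentence just before it names suicidal thoughts and self-harm as two separate items.

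**2. How wide the missing interval would be (illustration)**

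The documents give no self-harm rate, alpha, power or effect size, so there is no planned figure to reproduce. Inputs:

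- 100 youth in total (protocol section 6).
- 1:1 allocation, so 50 per arm: an assumption. No ratio is stated; section 30 only compares the allocation to a coin toss.
- 35 per arm as a low case: 50 × 0.70. The 70% is the share of adolescent assessments obtained at 16 months in a different trial (section 10, Prevention of Dropouts). It is not a forecast of T2 retention here.
- True rates of 30%, 50% and 70%, equal in both arms: an assumption.

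Half-width of the 95% interval for a risk difference = 1.96 × √(2p(1−p)/n).

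- n = 50, p = 0.30 or 0.70: 1.96 × √(0.42/50) = 0.180, or 18.0 points.
- n = 50, p = 0.50: 1.96 × √(0.50/50) = 0.196, or 19.6 points.
- n = 35, p = 0.30 or 0.70: 1.96 × √(0.42/35) = 0.215, or 21.5 points.
- n = 35, p = 0.50: 1.96 × √(0.50/35) = 0.234, or 23.4 points.

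**3. Why counts and denominators matter**

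Take 20% against 40%, a 20-point gap, with Newcombe (Wilson-based) 95% intervals for CIFFTA minus TAU:

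- 10/50 against 20/50: −36.4 to −2.0 points.
- 7/35 against 14/35: −39.2 to +1.5 points.

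The percentages are identical and the intervals are not. The example was picked so that one interval excludes zero and the other does not. It shows that denominators matter; it says nothing about this trial's result.

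**The case against.** The best defence comes from the protocol's own model of change. Section 4 (Background) says the study hopes to lower self-harm risk by producing effects on depression, emotion regulation, substance use and family functioning. The Measures text in section 10 calls self-harm an ultimate outcome and those factors immediate ones. Testing most of the immediate outcomes by arm, describing self-harm, and then relating mechanisms to self-harm partly follows that logic. The aim is also only preliminary efficacy, and with 100 youth a significance test on self-harm would be weak. This stands as a reason for caution about testing. It does not explain an absent interval, because section 9 still makes self-harm primary, the SAP gives no such rationale, and it tests other outcomes by arm at the same sample size.

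Some stronger readings are tempting but not supported:

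- A reader might infer that the arms are not compared on self-harm at all. They are, descriptively: the rates are by condition and the point difference follows by subtraction. What is missing is a named contrast and its uncertainty.
- A reader might infer that the rates cover only the clinical-range subgroup. The paragraph suggests it, but the sentence does not say so. The same doubt applies to the thoughts-of-suicide test, which sits in that paragraph and names no time point.
- A reader might infer that the endpoint is undefined. The SAP does not say whether past-month self-harm covers suicide attempts, non-suicidal self-injury or both, although protocol section 4 includes both in self-harm. Section 10 refers to attached measures, not available for this check, which may settle it.
- A reader might infer that self-harm was left untested because of its result. Nothing in the documents bears on motive.

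**Conclusion.** The point holds from the text alone. The sole primary endpoint, on a comparative aim, is compared by arm only through descriptive rates in a population that is not clearly stated. No analysis in the SAP gives an interval or test by arm for it. The protocol text available contains no statistical section that fills the gap, although some of its pages could not be seen.

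The size is illustrative: about ±18 to 20 points at 50 per arm, or about ±21 to 23 points at 35 per arm, if rates lie between 30% and 70% and allocation is 1:1. The conclusion does not depend on those assumptions. They show only that bare rates would conceal substantial imprecision.

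**What to change.** Required:

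1. Add a CIFFTA versus TAU comparison of past-month self-harm at termination (T2) in all randomised youth, analysed as randomised. T2 is used because the SAP defines the variable there.
2. Report counts, denominators and the number missing in each arm, and the risk difference with its 95% CI. A significance test is not needed.
3. Label the comparison as not prespecified in the 8/21/24 SAP.
4. State which youth the existing descriptive rates cover.
5. Say whether the same comparison will be given for the protocol's 12-month assessment (T3, section 10). The SAP's mechanism paragraph speaks of only two time points.
6. If the attached measures do not already settle it, state whether the variable covers suicide attempts, non-suicidal self-injury or both.

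Optional, as sensitivity analyses: covariate adjustment and missing-data modelling. Two cautions apply. A yes/no baseline item over the past six months cannot serve as a covariate, because entry requires youth to "self-report an act of self-harm in the past 6 months" and the item is therefore constant. Predictors of dropout alone are also a weak basis for a missing-data model, since those unrelated to self-harm remove no bias.

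The cost is small: some SAP wording and one short analysis of a variable already coded at termination in the full sample. The downsides are a wide interval on the primary result and the not-prespecified label, since prespecification cannot be restored.
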